10.1 Primary endpoint analysis of part I

The primary objective being the description of the PK characteristics of BT524 is not covered in great detail by this SAP. In the scope of this SAP, descriptive summary statistics, including changes from baseline for the fibrinogen antigen (from part I), will be provided for each age group (based on SAF, FAS, PP, and PK population). Values from each age group will be evaluated by a one-sample t-test (pre-/post-comparison) and presented in a tabular format.

A listing with all patient fibrinogen antigen (from part I) data will be also presented.

PK parameters defined for the primary objective will be derived from concentration-time profiles using adapted methodology, non-compartmental analysis, compartment analysis, or population modelling, as required. Details related to the analysis of these PK parameters will be specified in separate PK analyses plans.

10.2 Secondary endpoint analyses of part I

PD parameters defined for the secondary objective will be derived from concentration-time profiles using adapted methodology, non-compartmental analysis, compartment analysis, or population modelling, as required. Details related to the analysis of these PD parameters will be specified in separate PK analyses plans.

In the scope of this SAP, descriptive summary statistics, including changes from baseline for the fibrinogen activity (from part I), will be provided for each age group (based on SAF, FAS, PP, and PK population). Values from each age group will be evaluated by a one-sample t-test (pre-/post-comparison) and presented in a tabular format. Surrogate efficacy parameter MCF, assessed by fib-tem S, will be measured in part I pre-dose and at 1 and 8 hours post-end of each IV infusion in patients \geq 6 years. MCF will be measured pre-dose and at 1 hour post-end of infusion in children between 2 and $<$ 6 years and pre-dose and at the end of each infusion in children $<$ 2 years.

Descriptive statistics including change from baseline will be presented for each age group, i.e. $<$ 2 years, 2 to $<$ 6 years, \geq 6 to $<$ 12 years, 12 to $<$ 18 years, \geq 18 years (based on FAS, PP, and SAF population).

Values for the patients \geq 18 years will be evaluated by a one-sample t-test (pre-/post-comparison) and presented in a tabular format.

This analysis, done for both post-dosing time points, will be considered confirmatory for the 1 hour post-end of infusion assessment in patients \geq 18 years. Additionally, 95%-confidence levels will be calculated.

More precisely, the t-test will assess the mean difference $\mu_{1,0}$ between dependent measurements (1h post minus pre-treatment MCF difference; one sample) and test the null hypothesis $H_0: \mu_{1,0} < 0$ versus the alternative $H_1: \mu_{1,0} > 0$ at a two-tailed α -level of 0.05.

Correlation between MCF and fibrinogen activity pre-dose and at 1 and 8 hours post-end of each IV infusion will also be assessed in patients ≥ 6 years.

Note that (according to protocol section 14.4.5.2.5) consumption of BT524 (dose per kilogram body weight and total dose) during part I, calculated and presented in the framework of exposure and compliance (cf. section above), can also be assessed and interpreted as efficacy endpoint in respect to MCF.

Also the efficacy parameter MCF will be presented as a whisker box plot for FAS.

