# 15.2 Statistical Methods

The statistical planning and evaluation of the study will be carried out by a qualified statistician in accordance with the ICH-guidelines and adequate biostatistical SOPs. A more detailed description of the statistical analysis will be provided in the SAP. The SAP is to be finalized and approved prior to database lock.

All analyses of this open-label study will be performed on the intent-to-treat (ITT) as well as the per protocol (PP) population. ITT population will include all patients who received at least any portion of BT524. The PP population will include all patients who received at least 90 % of the planned total dose of BT524, met all inclusion and no exclusion criteria, complied with the protocol procedures and had no major deviations impacting on study analysis.

Statistical tests will be performed descriptively. Only the one test of a secondary efficacy endpoint of Part I (1-hour post-end to pre-value of MCF) is considered confirmatory. A p-value less than 0.05 will be considered statistically significant.

Only descriptive analyses will be performed to compare the efficacy results of study 984 with the results from published clinical trials (Manco-Johnson 2009 and Peyvandi 2006).

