### Part I

For analysis of PD, the same software will be used to determine the respective parameters with fibrinogen activity data.

Surrogate efficacy parameter MCF, assessed by fib-tem S, will be evaluated by a one sample t-test (pre-/post-comparison) and presented in a tabular format and/or graphical format. This analysis will be confirmatory for the 1 hour post-end of infusion assessment.

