2.1 Changes to the study protocol

The statistical analysis as specified in this SAP is consistent with the statistical analysis as specified in the study protocol (version 6.0).

In the study protocol age groups were defined to describe/define differences in time points of study assessments to be performed for different age groups (see flowchart of study in study protocol section 3). In the SAP age groups were defined differently for data analyses.

Shift tables specified in the study protocol for safety laboratory assessment will be not used.

No changes in the clinical study protocol were considered necessary by the Sponsor to handle clinical protocol deviations possibly related to the COVID-19 pandemic at the end of the study. It was therefore decided in the Blinded Data Review Meeting (BDRM) of June 25, 2020, that any non-conformities in the study conduct caused by the COVID-19 pandemic will be described in a note to file, and any COVID-19 related protocol deviation per patient will be listed in BDRM minutes and presented in study listings where appropriate.

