2.2 Changes to previous SAP versions

The first version of the SAP was based on study protocol version 4.0 and signed on 17-Sep-2015.

The amended SAP version 2.0 was intended to reflect the inclusion and treatment of children 0 to <6 years into the ongoing study 984. This extension of the ongoing study 984 was introduced within the study protocol version 5.0 after the positive opinion of the Paediatric Committee on the agreement of the Paediatric Investigation Plan (EMA-001931-PIP01-16) obtained in March 2017.

The amended SAP version 3.0 is intended to precisely describe the responsibilities of the different CROs to the analysis of the study. Definition of analysis sets was refined and PK population added for the descriptive analysis of PK within this SAP. For the age subgroups it was clarified how age of patients and bleeding events is calculated/defined for the respective analysis sets and study parts. Additional clarification for presentation of data was added where needed and the list of table shells in Appendix 15.1 was updated due to changes made.

3 Study Design

The present study is designed as a prospective, uncontrolled, open-label, multicentre, phase I/III study investigating the 14 day single-dose pharmacokinetic and pharmacodynamic properties, efficacy and safety of BT524 following intravenous administration in the treatment or prophylaxis of bleeding in patients with congenital afibrinogenemia or severe congenital hypofibrinogenemia.

The study is divided into two study parts (part I and part II), briefly described in the following:

Table 1: Overview of Study Design and Endpoints

PART I	PART II
	(Individual follow-up 49 ± 4 days after the last administration of BT524)
BT524 Single IV Infusion (70 mg/kg BW)	On-Demand Treatment (ODT) On-Demand Prophylaxis (ODP) BT524 Single or repetitive IV Infusion(s) as individually required
Pharmacokinetics (PK) Pharmacodynamics (PD)	Clinical Efficacy
n = 20 patients ≥ 6 to ≤ 75 years and at least 3 patients 0 to < 6 years In total: n = 23 patients (part I)	All patients who have completed part I (n = 23) and additional patients without PK/PD: at least 10 patients ≥ 6 to ≤ 75 years and at least 3 patients 0 to < 6 years In total (planned): n ≥ 36 patients (part II)
1-2 months	min. 12 months
Surrogate Efficacy	
Safety	

Part I

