3.1 Sample size estimation

The primary objectives of this study are key PK parameters. For the PK parameters no formal sample size calculation was carried out. As a general rule approximately 20 patients in this single cohort should suffice to calculate PK parameters with the corresponding range of distribution.

For the surrogate (secondary) efficacy variable MCF, a formal sample size calculation was performed. On the basis of a t-test assessing the difference between dependent means (post minus pre-treatment MCF difference; one sample) the sample size can be calculated. The mean MCF (measured by Fib-tem S of ROTEM) in the study population consisting of patients with congenital fibrinogen deficiency (i.e., a- or severe hypofibrinogenemia) will be determined prior to BT524 treatment and 1 hour after treatment.

With 15 patients, a pre-treatment mean of 4 mm (SD 7 mm) and a post-treatment mean of 10 mm (SD 8 mm) an effect size of 0.8 mm can be detected with a power of 80% at $\alpha = 5\%$ (2-sided) significance level.

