8.4 Compliance

For part I compliance can be assessed by the statistics on calculated dose of fibrinogen per kg (mg/kg) presented within the dosage evaluation (cf. section 8.2 above). For part I, analyses will use actual time, actual dose and infusion rate to derive the different characteristics.

Due to the individually tailored dose for treatment of part II bleeding events no compliance rules based on calculated dose as for part I treatments apply. As the IMP will be administered intravenously to each patient under the supervision of the study investigator or designated qualified study personnel, the compliance is expected to be 100%. In addition, compliance can be assessed based on infusion interruptions (cf. section 8.3 above).

9 Previous and Concomitant Medication or Treatment

All assessments will be done for part I and part II separately for the SAF set.

Previous and concomitant medications are coded according to WHO drug dictionary. version 2012Q3 which will be used at time of database lock and stored with A(natomical) T(herapeutic) C(hemical) codes and generic names.

Treatment will be classified as previous if stopped prior first infusion and as concomitant if overlapping with study participation after first infusion.

The numbers and frequencies of previous and concomitant medications will be given per ATC level 2. If a patient has received more than 1 drug within an ATC class he/she will be counted only once for this ATC class. A listing with all patient previous and concomitant medication or treatment will be also presented.

10 Pharmacokinetics, Pharmacodynamics and Efficacy

All assessments will be done for part I and part II separately.

Unless explicitly specified otherwise efficacy analyses will consist of descriptive methods and not test hypotheses but rather aim at parameter estimation and determination of confidence intervals. Should tests be conducted and/or p-values be given (beyond the one in section 10.2), note that these are not adjusted for multiplicity (which would be needed for fully confirmatory conclusions across all tests given the number of endpoints to investigate).

Also, only descriptive analyses will be performed to compare the efficacy results of study 984 with the results from published clinical trials (cf. protocol section 15.2).

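### SAP 10.2 limits the only confirmatory test (Part I MCF, 1 hour versus pre-dose) to adults, a change from the protocol that SAP 2.1 does not declare and that the 15-patient power statement does not reflect

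*SAP*

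**What the plan says.** Protocol 15.2 states: "Only the one test of a secondary efficacy endpoint of Part I (1-hour post-end to pre-value of MCF) is considered confirmatory". The Part I paragraph of Protocol 15.2.5 repeats it: "This analysis will be confirmatory for the 1 hour post-end of infusion assessment". Neither sentence restricts age.

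SAP 10.2 plans MCF descriptive statistics for every age group, but applies the one-sample t-test only to patients aged 18 or over. It then says the analysis "will be considered confirmatory for the 1 hour post-end of infusion assessment in patients" of that age. No reason is given. SAP 5.1 names the same single confirmatory test without a population, and the opening of SAP section 10 points to 10.2 for it: "Should tests be conducted and/or p-values be given (beyond the one in section 10.2), note that these are not adjusted for multiplicity".

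On changes from the protocol, SAP 2.1 says: "The statistical analysis as specified in this SAP is consistent with the statistical analysis as specified in the study protocol (version 6.0". It then lists three items: age groups ("In the SAP age groups were defined differently for data analyses"), the dropped laboratory shift tables, and the handling of COVID-19 deviations. SAP 2.2, on changes between SAP versions, says about age only: "For the age subgroups it was clarified how age of patients and bleeding events is calculated/defined for the respective analysis sets and study parts".

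SAP 3.1 repeats the protocol's sample-size statement: "With 15 patients, a pre-treatment mean of 4 mm (SD 7 mm) and a post-treatment mean of 10 mm (SD 8 mm", with 80% power at two-sided 5% for an effect size of 0.8. The protocol synopsis plans about 20 Part I patients aged 6 to 75 to obtain about 15 evaluable for PK/PD and the surrogate endpoint.

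**The concern.** The population of the only confirmatory test differs between the two documents, and the document that changed it says nothing has changed. SAP 2.1 records something as small as dropped shift tables, so a reader would expect to find this there. Defining age groups differently for analysis concerns subgroup boundaries. It does not tell the reader that patients under 18 leave the confirmatory test.

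The study is open-label, and the SAP carries a date of 2 July 2020, after the data review meeting of 25 June 2020. Nothing here shows that the limit was chosen with knowledge of results, but the documents do not show when or why it was set.

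The sample-size statement in SAP 3.1 was built on a cohort that includes minors, so it no longer describes the patients to be tested.

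**Working it through.** **1. Does sampling explain a cut at 18?** Protocol 14.4.5 and SAP 10.2 give these Part I MCF times:

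| Age | MCF samples | 1-hour value |
|---|---|---|
| 6 years and over | pre-dose, 1 h, 8 h | yes |
| 2 to under 6 years | pre-dose, 1 h | yes |
| under 2 years | pre-dose, end of infusion | no |

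The data support a lower limit of 2 years, not 18. SAP 10.1 and 10.2 also run pre/post t-tests in every age group for fibrinogen antigen and activity. Among these tests, only the one for MCF is confined to adults.

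**2. Reproducing the plan's figure.** Inputs from SAP 3.1: n = 15, means 4 and 10 mm, SDs 7 and 8 mm, two-sided alpha 0.05, effect size 0.8. The unit is printed as mm, but the figure works only as a standardised effect d = mean difference / SD of the difference. A 0.8 mm change in 15 patients would have about 6% to 9% power for correlations of 0 to 0.8.

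Power of the paired t-test comes from the noncentral t distribution with n − 1 degrees of freedom and noncentrality d√n. For n = 15 the noncentrality is 0.8 × √15 = 3.10 and power is 82.1%. Fifteen is the smallest n that reaches 80%, and the effect detectable at 80% with 15 patients is 0.778, which rounds to 0.8. The figure reproduces.

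The implied SD of the difference is 6 / 0.8 = 7.5 mm. The implied correlation is (49 + 64 − 56.25) / (2 × 7 × 8) = 0.507, which the documents do not state.

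**3. The same effect in adults only.** The number of evaluable adults is not given. Protocol 11.1.5 requires only the first 10 of about 20 patients to be adults.

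| n | Power at d = 0.8 |
|---|---|
| 10 | 61.6% |
| 11 | 66.8% |
| 12 | 71.4% |
| 13 | 75.4% |
| 14 | 79.0% |
| 15 | 82.1% |
| 20 | 92.4% |

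At the synopsis's evaluability of 15/20 = 75%, 15 evaluable adults need 15 / 0.75 = 20 adults, that is the whole planned cohort aged 6 to 75. Protocol 13.2 gives 9 November 2014 as first patient in for ages 6 to under 18. Protocol 11.1.5 also has the DMC review data from at least 3 children and 3 adolescents before any child under 6 is enrolled. If those six are Part I patients (not stated), at most 14 of 20 are adults. Power is then 79.0% if all 14 are evaluable. At 75% evaluability, 14 × 0.75 = 10.5, and 10 or 11 adults give 62% to 67%.

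**4. Sensitivity to the correlation r.** SD of the difference = √(49 + 64 − 112r), with a mean change of 6 mm:

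| r | SD of difference (mm) | Power, n = 10 |
|---|---|---|
| 0 | 10.63 | 35.8% |
| 0.25 | 9.22 | 45.2% |
| 0.5 | 7.55 | 61.1% |
| 0.75 | 5.39 | 87.9% |

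Ten adults reach 80% at r of about 0.685, and 14 adults at about 0.52.

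**5. A favourable case.** Protocol 14.4.5 expects MCF to be unmeasurable in these patients before treatment, and SAP 5.6 sets such values to 1 mm. If every pre-dose value were 1 mm and post-dose MCF were 10 mm (SD 8), d = 9 / 8 = 1.125. Power is then 77.9% with 8 adults and 88.5% with 10.

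**The case against.** The strongest reply accepts the mismatch and disputes its weight and the remedy.

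- **Power.** Neither Protocol 15.1 nor SAP 3.1 gives an age; the link to ages 6 to 75 comes from the synopsis. The 75% ratio may be pessimistic for a test that needs only two day-0 samples. If pre-dose MCF is essentially unmeasurable, 10 adults are enough. This stands: a loss of power is possible but not established.
- **Remaining information.** SAP 5.1 promises overall totals in general and 95% confidence intervals where appropriate. If applied to MCF, an all-ages interval would carry the same information as the test. This stands in part: these are general rules, and 10.2 names only age groups.
- **Which population.** Protocol 14.4.1 sets out the MCF comparison separately for patients aged 6 and over, 2 to under 6, and under 2, so a 6-and-over test would match the synopsis cohort. But the two protocol sentences that define the confirmatory test carry no age limit, and including ages 2 to under 6 can only add patients to the 15 planned.
- **Timing.** Changing the confirmatory population after data review invites criticism, so disclosure alone might be the safer course. That has force against a new choice, but returning to the protocol's population is not one.

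**Conclusion.** The concern holds. SAP 10.2 narrows the only confirmatory test to adults, the protocol does not, and SAP 2.1 declares consistency without listing the change. This rests on the text alone and needs no assumption. The mismatch is between the protocol and SAP 10.2; SAP 5.1 is silent on population and does not contradict 10.2.

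The effect on power is conditional on the number of evaluable adults and the correlation, neither of which is given. At d = 0.8, 80% power needs 15 evaluable adults, and no passage requires that many. The consequence for the trial is limited: the primary objective is PK, MCF is a secondary surrogate, and its change is still tabulated for every age group. It should be fixed.

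**What to change.** In SAP 10.2, run the confirmatory test on all Part I patients who have both a pre-dose and a 1-hour MCF value, and report the adults-only result as supportive. By schedule, only children under 2 drop out.

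If the adult restriction is kept, list it in SAP 2.1 as a change from the protocol and give the reason. In SAP 3.1, restate the power for the number of evaluable adults, together with the assumed SD of the paired difference.

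The cost is SAP wording and one population filter. No new data or patients are needed.

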10.3 Secondary endpoint analyses of part II

Each of the below secondary efficacy parameters will be evaluated and descriptive statistics presented on event level from part II (ODP or ODT, each for minor events, major events and overall) for the overall population and each age group. More precisely, the following efficacy parameters after each event will be assessed:

Overall haemostatic response to treatment with BT524 for each surgical procedure and each treated bleed as assessed by the investigator according to a 4 point scale ("none", "moderate", "good" or "excellent") will be evaluated presenting response rates with 95 % confidence intervals for each scale and for the sum of excellent and good, classified as success. These event-based evaluations will be conducted according to two concepts:

- 1) descriptively (showing frequencies and percentages based on the event level FBE and PPBE analysis set) considering each event as an individual case and
- 2) by modelling considering events as repeated measurements within the same patient (based on FBE and PPBE), if applicable (e.g. by general estimation equations with intra-patient correlation structure). Provided sufficient numbers of ODT and ODP, minor /major events should be considered (e.g. analysis by type according to concept 1 above).

Overall haemostatic response will also be presented in pie chart and listed.

For each surgical procedure loss of blood (intra- and postoperatively, re-bleedings) will be listed considering each event as an individual case (based on the event level FBE and PPBE analyses sets).

In addition, loss of blood is to be rated by the investigator according to classifications (loss of blood is below/within/above the expected range for the procedure performed) for surgical bleeding events. These ratings will be evaluated presenting numbers and percentages of events considering each bleeding event as an individual case (cf. concept 1 above).

Descriptive analysis on event level (based on event based FBE and PPBE analyses sets) will be conducted for and also listed

- Units of other fibrinogen-containing products infused besides BT524 (e.g., fresh frozen plasma or cryoprecipitate) given to counteract hemodynamic instability at the day of BT524 administration or 1 day after.
- Units of transfusion products infused, e.g., allogenic or autologous blood (packed red blood cells, fresh whole blood), platelets, given to counteract hemodynamic instability at the day of BT524 administration or 1 day after.

- Consumption of BT524 (dose per kilogram body weight, dose per infusion and total dose) required pre-, intra- or post-operatively for effective treatment of surgical bleeding events.
- Quality of wound healing assessed after wound healing is expected to be completed.

Furthermore, MCF as a surrogate efficacy parameter will be evaluated pre-dose and at 1 hour post-end of each IV infusion (including repetitive infusion for one bleeding event) by means of non-confirmatory t-test(s) pre/post comparison plus correlation between MCF and fibrinogen activity. Also MCF will be presented as a whisker box plot and also listed.

Descriptive summary statistics including changes from baseline for the fibrinogen activity will be provided for each age group. MCF and fibrinogen activity values from additional samplings (beside pre-dose and 1 hour post-dose) taken as required per investigator will be listed and not used in the analyses described above. These analyses will be conducted on event level, i.e. based on the event based FBE and PPBE analysis set. Otherwise, details correspond to those of part I analysis, except that the testing is considered as non- confirmatory.

With respect to the two evaluation concepts of efficacy, the concept when multiple events per patient are to be handled as individual cases is considered primary analysis within the framework of secondary analyses of part II.

Descriptive summary statistics and a listing for the fibrinogen antigen at screening will be provided for each age group on patient level (SAF, FAS, and PP analysis sets).

11 Safety

All assessments will be done for part I and part II separately.

APE-Set will be used to present overall numbers of AEs incl. NTEAEs. All safety analyses will be based on the SAF.

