### 14.4.2 Specifications of Clinical Efficacy Parameters

### PART II

Efficacy of BT524 will be assessed as **secondary objectives**.

The following efficacy parameters will be assessed after each bleeding event:

- Overall **hemostatic response** to treatment with BT524 for each surgical procedure and each treated bleed as assessed by the investigator according to a 4 point scale: "none", "moderate", "good" or "excellent"
- Total loss of blood (e.g., intra- and postoperatively, re-bleedings), if applicable
- Units of other fibrinogen-containing products infused besides BT524 e.g., fresh frozen plasma or cryoprecipitate
- Units of transfusion products infused, e.g., allogenic or autologous blood (packed red blood cells, fresh whole blood), platelets
- Consumption of BT524 (doses per kilogram BW required pre-, intra- or postoperatively for effective treatment)

The following efficacy parameter will be assessed after wound healing is expected to be completed:

• Quality of wound healing, if applicable

With respect to the evaluation of efficacy, patients with multiple events are to be considered as *individual cases* in a primary analysis.

14.4.3 Methods for Assessing, Recording and Analyzing Pharmacokinetic Parameters *14.4.3.1 Determination of Fibrinogen Antigen* 

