# PART II

The investigator is asked to classify any bleeding event (spontaneous bleeding, surgery, post traumatic bleeding) post-dose as minor or major (please refer to Appendix 20.3 *Recommendation for the 'Assessment of Bleeding Events'*). For each surgical procedure as well as for each treated bleed, the investigator will classify the overall hemostatic response to treatment with BT524 according to a 4 point scale as "none", "moderate", "good" or "excellent". The overall assessment is to be performed at the day of hospital discharge (if applicable) or at the end of the treated bleeding event.

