### PART II

Units of other fibrinogen-containing products such as fresh frozen plasma, cryoprecipitate or alternative commercially available fibrinogen concentrates given to counteract hemodynamic instability will be documented and evaluated for each bleeding event (e.g., surgical intervention).

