### Part II

Efficacy will be evaluated based on ODP and/or ODT of bleeding events (i.e. surgical procedures, spontaneous or post- traumatic severe bleeding). Response will be assessed by the investigator by means of a 4 point scale ('none', 'moderate', 'good', and 'excellent'). Response rates will be presented with 95 % confidence intervals both considering each event as an individual case and considering events as repeated measurements within the same patient, if applicable (e.g. by General estimation equations with intra-subject correlation structure). Additionally, type of surgery, loss of blood intra- and postoperatively, quality of wound healing, units of other fibrinogen-containing products, and units of transfusion products will be considered. Moreover,
the consumption of BT524 required for effective treatment (bleeding events; pre-, intra-, post-operatively) will be calculated. Furthermore, MCF as a surrogate efficacy parameter will be evaluated also in part II of the study (non-confirmatory).

Details will be described in the statistical analysis plan.

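### SAP 10.3 counts other fibrinogen products and transfusions only on the BT524 day or the next day; the protocol sets no day limit and the SAP does not declare the restriction

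*SAP*

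**What the plan says.** Protocol 14.4.2 lists units of other fibrinogen-containing products and units of transfusion products among the part II efficacy parameters, under the lead-in "The following efficacy parameters will be assessed after each bleeding event". The methods sections, 14.4.5.2.3 for alternative fibrinogen products and 14.4.5.2.4 for transfusion products, each say that products "given to counteract hemodynamic instability will be documented and evaluated for each bleeding event (e.g., surgical intervention". The part II paragraph of Protocol 15.2.5 adds that "units of other fibrinogen-containing products, and units of transfusion products will be considered". None of these places sets a day limit.

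SAP 10.3 does. The event-level analysis of other fibrinogen-containing products covers those "given to counteract hemodynamic instability at the day of BT524 administration or 1 day after". The transfusion item carries the same restriction: "platelets, given to counteract hemodynamic instability at the day of BT524 administration or 1 day after". No reason is given.

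SAP 2.1 states: "The statistical analysis as specified in this SAP is consistent with the statistical analysis as specified in the study protocol (version 6.0". It then names its departures, which concern age groups, laboratory shift tables and COVID-19 deviations. The window is not among them, nor is it mentioned in the version history in SAP 2.2.

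**The concern.** Need for other fibrinogen products or blood after BT524 is a sign that BT524 alone did not suffice. If such products are counted for two days around a dose and no longer, use on later days of the same event drops out of the planned event-level summaries. Part II is uncontrolled and open-label, so no comparator arm shares the same omission.

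The reader of the tables would not see this. Tables 14.2.2.2.1-4 and 14.2.2.3.1-4 have titles that present them as covering all events, and SAP section 3 describes the same endpoints without a window. The neighbouring endpoints are not cut this way. The overall haemostatic response is rated late (Protocol 14.4.5.2.1: "The overall assessment is to be performed at the day of hospital discharge (if applicable) or at the end of the treated bleeding event"), blood loss includes postoperative loss and re-bleeding, and wound healing is judged once healing should be complete. One event could show a later re-bleed in the blood-loss listing and no product use in these tables.

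**Working it through.** The documents state no rate, power or sample size for these endpoints, so there is no figure to reproduce. The check compares the time frames and then asks what they imply for the counts.

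**Time frames for one part II event**

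| Source | Period |
|---|---|
| Protocol 14.4.2, 14.4.5.2.3, 14.4.5.2.4, 15.2.5 | per bleeding event, no day limit |
| SAP 10.3, both product endpoints | calendar day of BT524 and the next day |
| SAP 5.5, event analysis time | Treatment Day 0 to the safety visit (Day 49 ± 4) |
| Protocol 14.4.5.2.1, response rating | discharge day or end of the treated event |

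**Coverage of the SAP's own event analysis time.** Day 0 to Day 49 is 49 + 1 = 50 calendar days. With ± 4 days it is 46 to 54.

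- One infusion: 2/50 = 4.0% (2/46 = 4.3%; 2/54 = 3.7%).
- Infusions on two or three non-adjacent days, if each one reopens the window: 4/50 = 8% or 6/50 = 12%. The safety visit is timed from the last infusion, so the true shares are slightly lower. For infusions on Days 0 and 2 the visit falls on Day 51, and the share is 4/52 = 7.7%.

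These are shares of days, not of product use.

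**Dependence on the length of the event.** For one infusion and an event lasting from Day 0 to Day L, the share of event days outside the window is 1 − 2/(L + 1). For assumed L = 1, 2, 7 and 14 this gives 0%, 33%, 75% and 87%. A short event loses nothing.

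**Direction.** Every product counted under SAP 10.3 for an event would also be counted under a per-event rule with no day limit. The reverse is not true. So, event by event, the windowed count is at most the protocol count, with equality when no later product is given.

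**Illustration of size, on assumed values.** Let r be the true share of events that need other products, and s the share of those events in which they are needed only outside the window. The tables would then show r × (1 − s).

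| r | s = 10% | s = 25% | s = 50% |
|---|---|---|---|
| 5% | 4.5% | 3.75% | 2.5% |
| 10% | 9.0% | 7.5% | 5.0% |
| 20% | 18% | 15% | 10% |

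Neither r nor s can be taken from the documents.

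**Ambiguity for repeat infusions.** SAP 10.3 does not say whether the first, any or the last infusion day anchors the window. If any infusion day counts, the loss is smaller than under a first-dose reading.

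**The case against.** The best defence is that the protocol names each bleeding event as the unit of analysis rather than defining a period. It gives no end date for these counts, and 15.2.5 leaves details to the SAP. Choosing a window was therefore within the SAP's remit, and a short one helps to attribute product use to the treated event. This stands in part: the SAP may set a window. It does not excuse giving no reason for the choice, or leaving it out of SAP 2.1 while claiming consistency. Attribution is already served by the purpose restriction, haemodynamic instability, which both documents carry.

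Several stronger readings are tempting, and the documents do not support them:

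- A reader might infer that late use is scored as zero. The SAP states no coding rule; it only leaves such use out of the event-level analysis.
- A reader might infer that late use is missing from every summary. SAP section 9 tabulates concomitant medication or treatment after first infusion with no two-day limit (Table 14.1.5.1.4, Listing 16.5.10), and Protocol 11.6 requires emergency use of these products to be recorded. That table is per patient and by ATC class, so it does not replace event-level units.
- A reader might infer that late use is hidden. SAP 5.1 lists all collected data, and Listing 16.8.2 covers these products on SAF II. However, the SAP 10.3 sentence that promises listing refers to the windowed items, so it is unclear whether 16.8.2 is unrestricted.
- A reader might turn day shares into missed use, for example 5/7 = 71% for a seven-day course or 12/14 = 86% for fourteen days. That needs a single infusion, an assumed course length and evenly spread use. The documents give none of these, and outpatient events may be discharged from 5 hours after infusion.
- A reader might infer that these endpoints exist to detect delayed re-bleeding. The protocol places re-bleeding under blood loss.

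**Conclusion.** The mismatch is real and undeclared. SAP 10.3 restricts two protocol efficacy endpoints to a window narrower than the protocol's per-event evaluation, the SAP's own event analysis time and the response rating. Followed as written, the eight event-level tables can equal or understate additional product use in part II, never overstate it.

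The size cannot be stated. It is nil if all such products are given by the day after BT524, and it shrinks if repeat infusions reopen the window. The illustrative values above show only how the result would scale. The effect is confined to descriptive secondary outputs; the one confirmatory test, MCF at 1 hour in part I, is unaffected. The point should be corrected because clinical efficacy is assessed only in part II and the error can run in one direction only. It does not show that any use was in fact missed.

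**What to change.** In SAP 10.3, for the main FBE and PPBE tables:

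- Count all products in the two categories from Treatment Day 0, taken as the whole calendar day so that products given earlier that day are kept, to the end of the event (discharge or the overall haemostatic response assessment). If that falls on Day 0, let the count run through Day 1, so that it does not drop below the supplementary row.
- Assign each product to one event only, and stop at Day 0 of any subsequent treated event. A cumulative count to the Day 49 visit is not advisable without this rule: Protocol 13.1.2.1 and 13.1.2.3 let a later event's visit serve the earlier one, so products could be charged to the wrong event or counted twice.
- Keep the Day 0-1 count as a labelled supplementary row, and state which BT524 day anchors it when infusions are repeated.
- State whether Listing 16.8.2 is unrestricted.
- If any restriction is retained, declare it with its reason in SAP 2.1 and in the table titles or footnotes.

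The cost is SAP wording and a changed date filter. The existing window already needs administration dates, so no new data collection should be required. If the final tables have already been produced, the event-long count can be added as an extra table marked as such.
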